4.1. Hypotheses

- 4.1.1. There will be no change in VAS scores for dysmenorrhoea, dyspareunia, dyschezia and persistent pelvic pain between baseline pain and after 8 weeks of treatment with PEA/PLD versus placebo.
- 4.1.2. There will be no difference in VAS scores for dysmenorrhoea, dyspareunia, dyschezia and persistent pelvic pain after 8 weeks of treatment between patients treated by PEA/PLD compared with placebo.
- 4.1.3. There will be no difference in VAS scores for dysmenorrhoea, dyspareunia, dyschezia and persistent pelvic pain between patients treated by PEA/PLD compared with placebo, 4 months' after surgery.
- 4.1.4. There will be no change in cellular and molecular markers in endometriotic lesions, blood and peritoneal fluid in patients treated by PEA/PLD compared with placebo.

4.2. Study Aims

To assess the efficacy of PEA/PLD as a potential pain reduction treatment for endometriosis related pain

4.3. Outcome Measures

Primary outcomes

- 4.3.1. To compare the change in dysmenorrhoea VAS score between PEA/PLD and placebo treatment in patients with endometriosis prior to laparoscopic surgical treatment.
- 4.3.2. To compare the change in dyspareunia, dyschezia and persistent pelvic pain VAS score between PEA/PLD and placebo treatment in patients with endometriosis prior to laparoscopic surgical treatment.

Secondary outcomes

- 4.3.3. To compare the change in dysmenorrhoea VAS score between PEA/PLD and placebo treatment at baseline and 4 months after laparoscopic surgery for endometriosis.
- 4.3.4. To compare the change in dyspareunia, dyschezia and persistent pelvic pain VAS score between PEA/PLD and placebo treatment at baseline and 4 months after laparoscopic surgery for endometriosis.

Study Name: Palmitoylethanolamide and polydatin effect on pain and dysmenorrhea in women scheduled for laparoscopic treatment of possible endometriosis: a double blind randomised controlled trial

Protocol Number: 1 Version 0.5, dated 29 September 2020

- 4.3.5. To compare the change in dysmenorrhoea, dyspareunia, dyschezia and persistent pelvic pain VAS score between PEA/PLD and placebo, before surgery, in patients without surgical evidence of endometriosis.
- 4.3.6. To compare the change in dysmenorrhoea, dyspareunia, dyschezia and persistent pelvic pain VAS score between PEA/PLD and placebo, at baseline and 4 months after laparoscopic surgery without evidence of endometriosis.
- 4.3.7. To compare the change of quality of life between PEA/PLD and placebo treatment in women with surgical evidence of endometriosis, before surgery and again after surgery.
- 4.3.8. To compare changes in cellular and molecular markers from endometriotic lesions, blood and peritoneal fluid samples between patients treated by PEA/PLD and placebo.
- 4.3.9. To correlate changes in VAS score with changes in cellular and molecular markers, in patients with endometriosis, treated by PEA/PLD and placebo.
- 4.3.10. To assess the side effects of PEA/PLD.

5. Study Design

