Protocol Number: 1 Version 0.5, dated 29 September 2020

Statistical Methods:	
Continuous variables will be summarised as means with standard deviation if normally distributed or median with interquartile range if not. Comparisons will be performed using t-tests and Mann Whitney U tests respectively.
 
Categorical variables will be summarised as proportions and comparisons performed using Chi-squared and Fisher exact tests. P values of <0.05 will be considered significant.
 
The impact of the PEA treatment on continuous outcome pain measures will be assessed using linear modelling adjusting for the effect of covariates including pre-treatment pain measures.

Subgroups:	
 • Patients treated by palmitoylethanolamide/ • polydatin 400 mg/40 mg • Patients treated by placebo • Patients with surgically proven endometriosis • Patients with surgically proven absence of endometriosis

Study Name: Palmitoylethanolamide and polydatin effect on pain and dysmenorrhea in women scheduled for laparoscopic treatment of possible endometriosis: a double blind randomised controlled trial

Protocol Number: 1 Version 0.5, dated 29 September 2020

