8.1. Sample Size Estimation & Justification

The sample size required for a one point difference on the numerical pain scale between PEA/PLD treatment and placebo in the change of each type of pain measured VAS score before (at recruitment) and at 4 months after surgery, and SD of 2 (based on a previous study performed by our team), was calculated to be 128 (64 in each group), based on an alpha of 0.05, power of 0.8 and two sided p-value. Allowing for a drop-out rate of 30%, and assuming that 30% of patients will not be found to have endometriosis on surgery, a total sample size required is 130 in each group (N=260).

If the participant withdraws prior to completing 6 weeks of medical treatment, she will be removed from the study.

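### Four pain scores are all primary outcomes, each at an unadjusted 0.05, with no hierarchy or success rule, so the error rate and power of the main claim are undefined

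*Protocol*

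**What the plan says.** Protocol 4.3 has two entries under primary outcomes. The first, 4.3.1, is "To compare the change in dysmenorrhoea VAS score between PEA/PLD and placebo treatment in patients with endometriosis prior to laparoscopic surgical treatment". The second, 4.3.2, is "To compare the change in dyspareunia, dyschezia and persistent pelvic pain VAS score between PEA/PLD and placebo treatment in patients with endometriosis", also before surgery. The synopsis repeats both as primary objectives, and the hypotheses in 4.1 treat the four scores together.

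The synopsis (Statistical Methods) sets one threshold for comparisons: "P values of <0.05 will be considered significant". Section 8.2 gives the tests and models but does not mention multiplicity.

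Section 8.1 starts from "The sample size required for a one point difference on the numerical pain scale between PEA/PLD treatment and placebo" and continues "in the change of each type of pain measured VAS score before (at recruitment) and at 4 months after surgery, and SD of 2". The result "was calculated to be 128 (64 in each group), based on an alpha of 0.05, power of 0.8 and two sided p-value" is then raised to 130 per arm: "Allowing for a drop-out rate of 30%, and assuming that 30% of patients will not be found to have endometriosis on surgery".

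Section 7.3 says that recruitment goes on until each group has 130 participants for the primary outcome, and that later withdrawals are not replaced.

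The protocol names no lead score, test order, division of alpha, or rule for what counts as a positive primary result.

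**The concern.** Four primary tests, each at two-sided 0.05, need a rule that turns four p values into one conclusion. Without one, a trial with a single significant score could be reported as positive on a primary outcome, although up to four chances were taken. Under the opposite rule, where all four must be significant, the chance of success is lower than the 0.8 a reader may take from 8.1.

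A split result is plausible here. The background (3.2) cites a meta-analysis that found clinically relevant improvement in pelvic pain and dysmenorrhoea, a limited effect on deep dyspareunia and no clinically relevant effect on dyschezia. If this trial produced the same pattern, the protocol would not say whether its primary objective had been met. That judgement would then be made with the results in view.

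**Working it through.** **Inputs from the protocol.** Four primary scores (4.3.1, 4.3.2); threshold 0.05 (synopsis); difference 1 point, SD 2, two-sided alpha 0.05, power 0.8, 64 per group, 30% dropout, 30% without endometriosis (8.1); 130 per group (synopsis, 7.3, 8.1).

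**Assumed.** Equal correlation between the four change scores, from 0 to 0.9. The protocol gives no value. For power, a true 1-point effect with SD 2 on every score at 8 weeks.

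**1. The plan's own figure.** Standardised difference d = 1/2 = 0.5. A two-sample t-test at two-sided 0.05 and power 0.8 needs 63.8, so 64 per group, where power is 80.1%. Inflation: 64/(0.7 × 0.7) = 130.6, against 130 stated. The figure reproduces, and it is for one score.

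**2. At least one false positive if any one score suffices.** With independent scores, 1 − 0.95⁴ = 0.185. Simulation of four equally correlated normal test statistics gives the rest:

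| Correlation | Chance of at least one false positive |
|---|---|
| 0 | 18.5% |
| 0.3 | 17.4% |
| 0.5 | about 15.6% |
| 0.7 | 13.0% |
| 0.9 | 9.4% |

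**3. Power if all four scores are required.** The error rate then cannot exceed 5%. Joint power depends on how many patients are evaluable, and two readings are open:

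- *Section 8.1:* both losses come out of 130, so 130 × 0.7 × 0.7 = 63.7, about 64 per arm. Per-score power is 80.1%. Independent scores: 0.801⁴ = 0.41. At correlation 0.7, simulation gives 0.62.
- *Section 7.3, read as replacing dropouts:* only the 30% without endometriosis are lost, so 130 × 0.7 = 91 per arm. Per-score power by t-test is 91.8%. Independent scores: 0.918⁴ = 0.71. At correlation 0.7, simulation gives 0.82.

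**4. Power if alpha is split equally.** Each score is tested at 0.05/4 = 0.0125. With 64 evaluable per arm, per-score power is 61.6%. Reaching 80% takes 90.8, so 91 evaluable per arm. On the 8.1 reading that means recruiting 91/0.49 = 186 per arm; on the 7.3 reading, 130 per arm already yields 91.

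**5. Time point.** The primary outcomes are measured before surgery, after 8 weeks of treatment. Section 8.1 sizes the change to 4 months after surgery, which is the time point of secondary outcomes 4.3.3 and 4.3.4. The false-positive figures do not depend on this. The power figures carry over to 8 weeks only under the assumption stated above.

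**The case against.** The strongest reply has four parts.

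**The analysis plan may settle it.** It is not shown, and test order or alpha allocation is often set there. This has some force against a complaint about missing detail. But the protocol itself fixes four outcomes as primary, an unadjusted threshold and a sample size that gives each score the full alpha. A later split of alpha would depart from the synopsis and from the basis of 8.1. Listing dysmenorrhoea first does not create a hierarchy, because both entries stand under the same heading.

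**A flat false-positive rate of 13–19% is not established.** A reader might infer that this is simply the trial's error rate. It holds only if one significant score is enough and the correlations lie between 0 and 0.7, and the protocol states neither. At correlation 0.9 the figure is 9.4%, and if all four scores are required it is at most 5%. This objection stands, so the figures must be given as conditional.

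**Section 8.1 does not promise 80% power for the primary objective as a whole.** Its power refers to the difference "in the change of each type of pain measured VAS score". To say that 80% holds only score by score therefore restates 8.1 and does not refute it. This stands too.

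**Joint power need not be far below 0.8.** On the 7.3 reading it is 71–82%, and an equal split of alpha already has 80% power per score. This stands as one of two readings. Sections 7.3 and 8.1 do not agree on how many patients remain, so neither range can be given alone.

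**Conclusion.** The point holds in a conditional form. The protocol fixes four unadjusted primary outcomes and gives no rule for combining them, so neither the error rate nor the power of the main claim is defined.

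- **Any one score suffices:** the false-positive chance is about 18.5% for independent scores, falling to 13% at correlation 0.7 and 9% at 0.9. It is nearly twice the nominal 5% or more over the range examined.
- **All four are required:** the error rate is controlled, and joint power for correlations 0 to 0.7 is 41–62% with 64 evaluable per arm, or 71–82% with about 91.

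All of this rests on assumed equal correlations. The power figures also assume a 1-point difference and SD of 2 on every score at 8 weeks. The documents do not support saying that 8.1 miscalculates. Its 64 per group is right for one score, and what it leaves open is which score and which time point that number is meant to protect.

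**What to change.** Amend the protocol before unblinding:

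1. In 4.3 and the synopsis, name the change in dysmenorrhoea VAS from baseline to 8 weeks as the single primary outcome, tested at two-sided 0.05. It is already listed first and appears in the trial title.
2. Make dyspareunia, dyschezia and persistent pelvic pain key secondary outcomes, tested by the Holm procedure and only if dysmenorrhoea is significant.
3. State in 8.1 that the power refers to this one score, and align its time point to 8 weeks. Say whether the 1-point difference and SD of 2 are also expected there. The protocol does not show this, so unchanged power cannot simply be asserted.

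**Cost.** Wording only. N stays at 260, and no visits or data are added. The sponsor gives up the option of claiming success on another score when dysmenorrhoea is not significant. Keeping four primary outcomes with an equal split of alpha is possible, but on the 8.1 reading it needs about 186 per arm, 372 in total, for 80% power per score.

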5.1. Study Type & Design & Schedule

STUDY TYPE

Multi-centre prospective double-blind placebo-controlled randomized trial

METHODS

Patients will be identified through the Gynaecology 2 Unit outpatient clinic at the RWH, the Endosurgery Gynaecology clinics at the Mercy hospital for women, and associated private practices in Victoria. Referrals and patient histories will be screened by a specialist gynaecologist, fellow trainee or research assistant prior to clinic to identify potential participants. The study will be explained to potential participants. Patients who give their consent will be blindly randomized to receive either PEA/PLD 400 mg/40 mg or placebo. Following randomization, all participants will be asked to complete a NECST questionnaire including a set of pain VAS scales, Quality of life tool (see details in Study methodology). The same questionnaire, with additional questions regarding adverse side effects and treatment compliance, will then be filled 8 weeks later (still before surgery), and 4 months' after surgery. The questionnaire will be available online and as hard copy.

Surgery will then take place as planned with surgical samples for immunohistochemistry and RNA taken only from the Royal Women's Hospital recruited patients. Samples will be collected as described in "Study methodology".

A total number of 260 patients will be recruited, 130 in each arm.

STUDY TABLE

Study Name: Palmitoylethanolamide and polydatin effect on pain and dysmenorrhea in women scheduled for laparoscopic treatment of possible endometriosis: a double blind randomised controlled trial

Protocol Number: 1 Version 0.5, dated 29 September 2020

Assessment/Procedure	Recruitment	After 8 weeks of treatment (pre surgery)	day of surgery	4 months' After surgery
Informed Consent	x			
Baseline Questionnaire	x			
Follow up questionnaire		x		x
Laparoscopy tissue collection (endometrium, endometriosis, blood and peritoneal fluids at RWH only) and Surgeon report			x	

Study Name: Palmitoylethanolamide and polydatin effect on pain and dysmenorrhea in women scheduled for laparoscopic treatment of possible endometriosis: a double blind randomised controlled trial

Protocol Number: 1 Version 0.5, dated 29 September 2020

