5.4. Study methodology

All subjects will be given oral and written information about the study and informed written consent will be obtained by our Research Nurses / Assistant (see attached patient information and consent forms). After consent has been obtained, an initial questionnaire will be completed by the women. The questionnaire includes demographic details, medical background, pain questions about menstrual pain and other pelvic pain symptoms including dysmenorrhoea, deep dyspareunia, dyschesia, daily pain and quality of life assessment.

Quality of life domains will include physical and mental health.

Recruited patients will then be blindly randomized to receive either PEA/PLD 400 mg/40 mg or placebo twice daily for 8 weeks.

Treatment will be prepared by a specialist compounding pharmacy in the form of similar capsules for PEA/PLD and placebo, distributed in similar containers with their content only known to the pharmacists.

The same questionnaire (without the demographic and medical history part) will then be filled at the end of 8 weeks of treatment (still before surgery) with additional adverse drug side effects and treatment compliance assessment.

Surgery will take place within 2 weeks of finishing the study treatment.

Final questionnaire will be sent to participants 4 months' after the surgery to evaluate pain and quality of life.

Collection of tissue Samples and clinical/medical Information

Only patients operated on at the Royal Women's Hospital will be consented for tissue/ biofluid collection. Patients operated at the Mercy Hospital for Women or private hospitals will have their surgeries as planned without any other surgical intervention.

Blood: During surgery, blood samples (25-50 mls, or 1¼ -2½ tablespoons) will be drawn and processed in the laboratories at the RWH.

Endometrial Biopsy: A routine endometrial biopsy will be collected from each woman. The biopsy will be collected following collection of a clinical biopsy during hysteroscopy (endometrial biopsies will only be collected from women providing clinical consent for an endometrial biopsy as part of her planned medical procedure). Endometrial samples will be histologically assessed for cycle stage and some will be stored in RNA later (Life Technologies) for mRNA (NGS analysis) or protein expression studies or used immediately in in vitro cell culture studies.

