Endometriotic lesions/cysts and peritoneal tissue: Two small samples of endometriotic lesion tissue will be taken by scissors (not diathermy) as fresh tissue and 1) stored in RNALater for RNA extraction (NGS analysis) and 2) stored in tissue media on ice for immediate in vitro cell culture studies. The formalin fixed lesions sample(s) collected as part of the routine histopathology process and diagnosis, will be accessed for research following routine histopathology assessment.

All other endometriosis lesions will be excised routinely by monopolar diathermy and submitted for routine histopathology. Paraffin embedded ectopic endometrium or peritoneum will only be recalled from pathology following completion of histopathological review (i.e. excess to pathology diagnostic requirements).

Peritoneal Fluid: a sample of peritoneal fluid (up to 10 ml) will be removed for research purposes and frozen for later use. If peritoneal fluid is not found, a saline light wash of

Study Name: Palmitoylethanolamide and polydatin effect on pain and dysmenorrhea in women scheduled for laparoscopic treatment of possible endometriosis: a double blind randomised controlled trial

Protocol Number: 1 Version 0.5, dated 29 September 2020

the pelvis will be done. This does not pose any additional risk for the patient except for extending surgical time by another 1-2 minutes. Samples will be stored at -80°C.

If no active endometriosis is seen, a small biopsy for histological assessment, immunohistochemistry and RNA analysis will be taken by scissors from one of the utero-sacral ligaments.

Surgeons will complete a dedicated operation report on surgical findings immediately after surgery, staging the endometriosis based on the revised American Society for Reproductive Medicine classification of endometriosis (rASRM).

Surgery and post-operative care will otherwise be unaffected by participation in the study. All surgeons and study investigators will be blinded to the patient's allocation to treatment or placebo groups.

Patients will be asked to complete a repeat questionnaire at 4 months' time after surgery.

Tissue bank samples: Endometriotic lesions and endometrium will be stored in RNALater for molecular analysis and/or formalin fixed for routine pathology. Tissues will be stored in the research precinct or recalled from pathology.

Menstrual cycle stage will be determined by pathology.

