All data will be collated into REDCap database, which is a secure, web-based application for building and managing complex data currently hosted at the University of Melbourne. Only coded data will be included in the RedCap database; no identifying information will be added.

Study Timeframe

Women scheduled to undergo laparoscopy for suspected endometriosis will be recruited from gynaecology outpatient clinics and prior to surgery at the Royal Women's Hospital, Melbourne (80 patients / year), the Mercy Hospital for Women (50 patients / year) and private rooms. We aim to collect approximately 130 samples per year. This number presumes average surgical volumes of laparoscopy for pelvic pain for suspected endometriosis, accounting for a 30% non-participation rate in eligible participants at each site. Recruitment should take approximately 2 years.

Data analysis and write up will take approximately 12 months.

Total 3 years after recruitment begins to complete the study.

[figure not shown]
6. Study Population

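### Outcome 4.3.9 correlates pain change with a change in markers, but every specimen is taken once, at surgery, so no marker change exists to correlate

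*Protocol*

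**What the plan says.** Protocol section 4.3 lists two secondary outcomes on markers. Outcome 4.3.8 is "To compare changes in cellular and molecular markers from endometriotic lesions, blood and peritoneal fluid samples between patients treated by PEA/PLD and placebo". Outcome 4.3.9 is "To correlate changes in VAS score with changes in cellular and molecular markers, in patients with endometriosis, treated by PEA/PLD and placebo". The synopsis repeats them as secondary objectives 6 and 7. Hypothesis 4.1.4 also speaks of no change in markers, on PEA/PLD compared with placebo.

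The study table in section 5.1 has one row for specimens, "Laparoscopy tissue collection (endometrium, endometriosis, blood and peritoneal fluids at RWH only) and Surgeon report", and its only mark is under the day of surgery. The procedures table in section 5.2 agrees. Section 5.4 gives the detail for each specimen:

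- blood: "During surgery, blood samples" are drawn;
- endometrium: a biopsy during hysteroscopy, which the study table places on the day of surgery;
- lesions: "Two small samples of endometriotic lesion tissue will be taken by scissors (not diathermy) as fresh tissue";
- peritoneal fluid: "a sample of peritoneal fluid (up to 10 ml) will be removed for research purposes and frozen for later use".

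On who is sampled, section 5.4 says: "Only patients operated on at the Royal Women's Hospital will be consented for tissue/ biofluid collection". Under its timeframe heading it gives 80 patients a year at the Royal Women's and 50 at the Mercy, names private rooms without a number, and adds: "We aim to collect approximately 130 samples per year".

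**The concern.** A change needs two values for the same woman. The schedule gives two or more for the pain score but only one for any marker. Outcome 4.3.9 pairs the two changes within women, so one member of the pair is missing for everyone. This is not a detail that an analysis plan can settle, because no analysis can supply a specimen that the schedule never collects.

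Half of the study question in the synopsis asks which cellular and molecular mechanisms the treatment modifies. If a level at surgery is analysed but reported under the wording of 4.3.9, a reader would take it as evidence that markers moved together with pain. A woman with a low marker level at surgery may simply have had a low level before treatment.

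**Working it through.** **1. The plan's own figures.** Section 8.1 sizes the trial for the pain score only. With a difference of 1, SD 2, two-sided alpha 0.05 and power 0.80:

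- n per arm = 2 × (1.960 + 0.842)² × 2² / 1² = 62.8, so 63 by the normal approximation; the t-test version gives 63.8, so 64 as stated;
- allowing for 30% drop-out and 30% without endometriosis: 64 / (0.7 × 0.7) = 130.6 per arm, against 130 stated.

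These figures reproduce. The protocol gives no sample size for the marker outcomes.

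**2. Measurement times (sections 5.1, 5.2, 5.4).**

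| Quantity | Recruitment | Week 8 | Surgery | 4 months after | Change within a woman |
|---|---|---|---|---|---|
| Pain VAS | yes | yes | no | yes | exists |
| Blood | no | no | yes | no | none |
| Endometrium | no | no | yes | no | none |
| Lesion tissue | no | no | yes | no | none |
| Peritoneal fluid | no | no | yes | no | none |

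Women with a marker change: 0 of 260.

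**3. Can the level stand in for the change?** Only in part. Suppose a marker had equal variance before and after treatment, with correlation ρ between the two (an assumption; the protocol gives no value). Then the correlation between change and final level is √((1 − ρ)/2):

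- ρ = 0.2: 0.63
- ρ = 0.5: 0.50
- ρ = 0.8: 0.32

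The more stable a marker is within women, the less its level at surgery says about its change.

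**4. How many women have lesion tissue?** Assume that the Royal Women's recruits at its stated rate for the stated two years: 80 × 2 = 160.

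- With endometriosis: 160 × 0.7 = 112, or 56 per arm.
- With the 30% drop-out also applied: 112 × 0.7 = 78.4, about 78, or 39 per arm.

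The 30% drop-out in section 8.1 belongs to a calculation on the pain score at 4 months after surgery. Women lost after surgery still have tissue, so 78 and 112 bracket the number.

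Detectable at 80% power, two-sided 0.05 (t-test for the standardised difference; r = tanh[(1.960 + 0.842)/√(n − 3)] for the correlation):

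| Royal Women's total | Women with lesions | Standardised difference | Correlation |
|---|---|---|---|
| 160 | 112 | 0.53 | 0.26 |
| 160 | 78 | 0.64 | 0.31 |
| 80 | 56 | 0.76 | 0.37 |
| 80 | 39 | 0.92 | 0.44 |

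The rows for 80 show what happens if other sites supply more of the 260.

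**5. The figure of 130 samples a year.** 80 + 50 = 130, and 130 × 2 = 260, the trial total. The sum includes the Mercy's 50, who give no specimens under section 5.4. The figure therefore fits participants, not specimens.

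**The case against.** The strongest reply is that the word is loose and the aim is sound. The background (section 3.2) describes the marker aim as a difference between PEA/PLD and placebo. Because the arms are randomised, comparing levels at surgery validly estimates the treatment effect on markers. This stands for 4.3.8, objective 6 and hypothesis 4.1.4. A reader might infer that both marker outcomes fail, but the documents support that only for 4.3.9. There the looser reading does not help: the same word would have to mean a within-woman change for the pain score and a level for the marker, in one sentence.

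Four other readings are tempting and go too far.

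- *Sampling at one site removes the change.* It does not. It limits numbers and confines the marker analysis to one randomisation stratum. The single time point is what removes the change.
- *The plan expects tissue from 130 women a year.* The sentence sits in a recruitment paragraph, doubles exactly to the trial total, and sections 5.1, 5.2 and 5.4 all restrict sampling to the Royal Women's. It is most likely a slip for participants.
- *The marker analysis will have 39 women per arm.* That depends on the assumed 160 and on applying all the drop-out before surgery. Private rooms recruit at an unstated rate, which could lower the number. Section 7.3 keeps recruiting until 130 per group are available for the primary outcome, which could raise it. The figure also covers lesions only, while 4.3.8 includes blood and fluid and is not limited to women with endometriosis.
- *The correlation will be pooled over arms without adjustment.* Outcome 4.3.9 does not say so, and the method may properly be left to an analysis plan.

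**Conclusion.** Outcome 4.3.9 and objective 7 are wrong as written: the marker change they need exists for no participant. This follows from the sampling schedule and depends on no assumed number. Outcome 4.3.8, objective 6 and hypothesis 4.1.4 need clearer wording, but what they aim at can be estimated validly. The primary pain outcomes, the sample size and the randomisation are unaffected.

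The precision of the marker analyses can be given only as a range. On an assumed 160 Royal Women's participants, 39 to 56 women per arm have lesion tissue, with a detectable standardised difference of about 0.64 to 0.53. A smaller Royal Women's share makes this worse. The correction is worth making because it alters what the trial may conclude about mechanism.

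**What to change.** - Reword 4.3.8, objective 6 and hypothesis 4.1.4 as the difference between arms in marker levels at surgery, in Royal Women's participants.
- Reword 4.3.9 and objective 7 as the association of the baseline-to-week-8 VAS change with marker level at surgery, adjusted for arm and baseline VAS, in Royal Women's participants with endometriosis. Make no claim of marker change within women. Adjusting for arm is a safeguard: a treatment effect on both pain and marker could by itself produce a correlation.
- In the timeframe text of section 5.4, say that the 130 a year are participants (80 + 50) and that only Royal Women's patients give specimens. If an expected number with lesion tissue is stated, give it as a range with its assumptions.
- Define the sampled group one way: section 5.1 refers to women recruited at the Royal Women's, section 5.4 to women operated on there.

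The cost is protocol wording and a weaker mechanistic conclusion from 4.3.9. No new sampling is needed. A pre-treatment blood sample would give a true change for blood markers at the price of an extra procedure, but it is not realistic for lesions or peritoneal fluid.
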